#### **7.1.2. Dosing Period**

The dosing period begins on the first day of dosing with study treatment (Day 0) and continues for a minimum of 104 weeks. Subjects will transition onto the OLE within 2-3 infusions from the approval of the amendment. Subjects will receive study drug every 2 weeks.

The visit window for all dosing visits is  $\pm 2$  days. Visits should be scheduled based on the previous visit, not the baseline visit.

Assessments and procedures to be performed during the dosing period are presented in [Section 16](#).

Muscle or pulmonary function tests that cannot be performed or produce inadequate results according to test procedures during a specified visit should be performed by the next scheduled dosing visit.

MRIs may be performed within  $\pm 2$  weeks of the specified visit.

Blood samples will be drawn for pharmacokinetic analysis according to the schedule in [Appendix 5](#). Blood draws to be collected on non-dosing days may be collected within  $\pm 1$  day as outlined in Appendix 5.

#### **7.1.3. End of Treatment**

Assessments and procedures to be conducted after the last dose of study drug on the main study are presented in [Appendix 4](#).

All subjects who complete 104 weeks of treatment will be offered continued participation via the OLE. If the subject consents to ongoing treatment, the EOT MRIs must be performed within 7 days of EOT.

#### **7.1.4. Early Withdrawal from Treatment and Safety Follow-up Period**

Subjects who prematurely discontinue the main study should be strongly encouraged to complete the final efficacy evaluations scheduled for Week 208/EOT as applicable, and the safety follow-up evaluations scheduled for the Week 210/EOS visit (4 weeks following the last dose).

Subjects who withdraw prior to week 104 will not be eligible to participate in the OLE.

#### **7.1.5. Safety Follow-Up Period**

For all subjects, the final safety assessments should be completed 4 weeks ( $\pm 7$  days) after the last dose of pamrevlumab, and subjects will receive a final safety follow-up phone call 60 days (+ 3 days) after the last dose.

#### **7.1.6. Missed Visits**

Every attempt must be made to complete all study visits as outlined in the Schedules of Assessments. Missed infusions will not be replaced. If a subject misses a scheduled efficacy

assessment, the assessment should be performed as soon after the missed visit as feasible and within the windows specified above.

#### **7.1.7. Unscheduled Visits**

Unscheduled Visit assessments may be required at the discretion of the investigator.

### **7.2. Assessments (Main Study)**

Please refer to the Schedules of Assessments for the main study for the scope and timing of assessments. Please refer to the Laboratory Manual for details regarding laboratory sample collection and processing; and the Study Reference Manual for details regarding the conduct of functional tests and MRIs.

#### **7.2.1. Pulmonary Function Tests**

The following pulmonary function tests (PFTs) will be performed to assess changes in lung function: forced vital capacity (FVC), maximal inspiratory pressure (MIP), maximum expiratory pressure (MEP) and peak expiratory flow rate (PEF; PEFR), forced expiratory volume in 1 second (FEV1), and peak cough flow ([Mayer, 2015](#), [Miller, 2005](#)).

#### **7.2.2. Muscle Strength and Functional Measurements**

The following assessments will be performed to assess changes in upper extremity strength and function: Brooke Upper Extremity Rating Scale (Brooke Scale), Performance of the Upper Limb (PUL), Grip Test, and Pinch Strength Test.

#### **7.2.3. Cardiac MRI**

Cardiac MRIs will be performed as per [Section 16](#) to assess changes in left ventricular ejection fraction (LVEF) and presence of late gadolinium enhancement (LGE), a marker for myocardial fibrosis.

#### **7.2.4. Muscle MRI**

An upper arm muscle MRI at screening, will be conducted within the screening period (4 weeks prior to Day 0) or anytime up to Week 4 dosing visit (4 weeks after Day 0). The results of this assessment are acceptable as baseline assessment.

Upper arm (bicep) muscle MRIs will be performed as per Section 16.

#### **7.2.5. Quality of Life Questionnaire**

Pediatrics Outcomes Data Collection Instrument (PODCI) Quality Outcome Questionnaire will be performed to assess if treatment with pamrevlumab improves quality of life.

#### **7.2.6. Vital Signs and Physical Examinations**

A physical examination will be performed at screening and baseline (Day 0), approximately every 12 weeks and at Week 208/EOT. Complete physical exams will be performed at screening, Week 48, Week 104, Week 156, and Week 208/ EOT. Other examinations may be disease-specific or problem-oriented examinations.

Vital signs (pulse, respiration, sitting blood pressure, and temperature) will be collected at screening and at all visits. During infusion visits, vital signs will be collected prior to start of each infusion, within 15 minutes of the end of each infusion, and within 15 minutes of the completion of the post-infusion observation period.

### **7.2.7.     Laboratory Assessments**

All laboratory tests of blood and/or urine specimens will be performed at a central laboratory or FibroGen, as appropriate. A Central Laboratory Manual with instructions on specimen collection, processing, storing, and shipping to the central laboratory will be provided to all participating sites.

Local clinical laboratories will be used to assess and facilitate the management of adverse events and to provide usual standard of care (including blood draws required prior to MRIs). Local clinical laboratory data will not be collected in the study database except for hematocrit values provided with imaging data.

#### **7.2.7.1.    Safety Assessments**

Blood samples will be drawn for the following analyses: complete blood count, gamma glutamyl transferase (GGT), total bilirubin, alkaline phosphatase (ALP), aspartate transaminase (AST), alanine transaminase (ALT), and albumin, creatine kinase (CK), and cystatin C.

Safety labs will be drawn at the site's local lab prior to MRIs to ensure there is no contraindication to MRI. Hematocrit should be included in the local lab draw as these results are required to assess fibrosis and will be provided to the central imaging vendor along with the MRI scans. Details are included in the Imaging Manual.

#### **7.2.7.2.    Pharmacokinetics**

Plasma concentrations of pamrevlumab will be determined on Day 0 pre-dose and within 1 hour post infusion, then on Days 2, 4, 7, 10, and 14. The Day 14 sample should be on the same day of, but prior to the start of the next infusion of study drug.

Day 2, 4, 7, and 10 PK assessments represent target days following the first dose; however, actual sample collection time of up to  $\pm 1$  day of the target time is acceptable as long as the actual time of dosing and actual time of each sample collection are recorded accurately.

At Weeks 26 and 52, trough pamrevlumab levels (Cmin) will be determined prior to study drug infusion.

PK samples will also be drawn within 60 minutes of infusion completion at Week 52.

#### **7.2.7.3.    Plasma and Urine CTGF**

Plasma and urine samples will be analyzed for CTGF concentrations from samples taken as described in [Appendix 5](#).

#### **7.2.7.4.    HAHA**

Blood samples will be drawn for analysis of human anti-human antibody (HAHA) according to the schedule in [Appendix 5](#).

#### **7.2.7.5. Biomarkers**

Blood samples will be drawn for analysis of biomarkers according to the schedule in [Appendix 5](#). The exact biomarkers will be based on current scientific knowledge regarding CTGF, pamrevlumab and DMD at the time the tests are performed. No genetic testing will be performed.

## 8. ASSESSMENT OF SAFETY

### 8.1. Background

Adverse event reports from investigators are the critical building blocks to the development of the safety profile of the Study Drug. Subjects will be asked non-leading questions in general terms to determine the occurrence of AEs, according to the schedule outlined in [Section 16](#). In addition, all AEs reported spontaneously during the course of the study will be recorded. The investigator must immediately (within 24 hours of awareness) report to the sponsor or designated safety management vendor all SAEs, regardless of whether the investigator believes they are related to the Study Drug.

### 8.2. Definitions

#### 8.2.1. Definition of an Adverse Event (AE)

For the purpose of this study, an AE is any untoward medical occurrence that occurred in the protocol-specified AE reporting period, and which does not necessarily have a causal relationship with the study drug. An AE includes medical conditions, signs, and symptoms not previously observed in the subject that emerge during the

protocol-specified AE reporting period, including signs or symptoms associated with an underlying condition that were not present prior to the AE reporting period ([Section 8.3.1](#)).

#### 8.2.2. Definition of a Serious Adverse Event (SAE)

A serious adverse event is any adverse event or suspected adverse reaction that results in any of the following outcomes:

- Death,
- A life-threatening AEs (i.e., if in the view of the investigator or sponsor, the subject was at immediate risk of death at the time of the event). Life-threatening does not refer to an event which hypothetically might have caused death if it were more severe,
- Inpatient hospitalization or prolongation of existing hospitalization,
- A persistent or significant incapacity or substantial disruption of the ability to conduct normal life functions,
- A congenital anomaly or birth defect, or
- Is considered a medically important event not meeting the above criteria, but which may jeopardize a subject or may require medical or surgical intervention to prevent one of the other criteria listed in this definition. Examples of such medical events include allergic bronchospasm requiring intensive treatment in an emergency room or at home, and blood dyscrasias or convulsions that do not result in inpatient hospitalization.

Please note that death is an outcome, not an event; the cause of death would be the adverse event.

Surgical procedures, *per se*, are not SAEs. The condition requiring the surgical procedure, however, may be an SAE.

Scheduled hospitalization or prolongation of a hospitalization due to standard of care assessments and procedures do not warrant reporting as adverse events unless resulting observations are deemed by the Investigator to meet the definition of an adverse event.

### **8.2.3. Definition of an Infusion Reaction**

Infusion reactions are immunologic reactions to an infused protein, and are different from events resulting from the process of infusing the protein (e.g., infusion site bruise) and are different from adverse events due to the infused protein's intended or unintended pharmacologic effects.

### **8.2.4. Acute Infusion Reaction**

An acute infusion reaction is one that meets both of the following criteria:

1. Occurs during or within 1 hour after infusion; and
2. Clinical manifestations consistent with:
  - a. IgE-mediated and non-IgE mediated hypersensitivity reactions, including but not limited to urticaria, skin rashes, angioedema, laryngeal edema, bronchospasm, gastrointestinal symptoms and hypotension; or
  - b. Cytokine release syndrome, including but not limited to fever, respiratory symptoms without the presence of wheezing, tremors, chills, flushing, pruritus, changes in blood pressure, dyspnea, chest discomfort, back pain, nausea, vomiting, diarrhea, and skin rashes.

#### **8.2.4.1. Delayed Infusion Reaction**

A delayed infusion reaction is one that meets both of the following criteria:

1. Occurs  $\geq 1$  hour after the infusion
2. Clinical manifestations as described above.

#### **8.2.4.2. Reporting Possible and Confirmed Infusion Reactions**

Both acute and delayed infusion reactions will be captured as AEs and also be reported to the medical monitor within 24 hours. See Study Reference Manual for additional details.

### **8.2.5. Special Situations**

Certain safety events, called 'Special Situations' that occur in association with the study drug(s) include, but are not limited to:

- Overdose of the medicinal product
- Suspected abuse/misuse of the medicinal product
- Inadvertent or accidental exposure to the medicinal product
- Medication error involving the medicinal product (with or without subject/patient exposure to the Sponsor medicinal product, e.g., name confusion)
- Drug-drug interaction

Special Situations will be reported to the sponsor or designated vendor within 24 hours on a Medication Error report form. See Study Reference Manual for details.

### **8.3. Procedures for Eliciting, Recording, and Reporting Adverse Events**

#### **8.3.1. Adverse Event Reporting Period**

The study period during which all AEs and SAEs must be reported begins after informed consent is obtained and ends 4 weeks after the last dose of study drug, except for pregnancy reporting ([Section 8.3.6](#)). In addition, all AEs reported spontaneously by the subject to site personnel, outside the study period, may be recorded. The investigator should notify FibroGen of any death or other SAEs occurring after a subject has discontinued or terminated study participation that may reasonably be related to this study ([Section 8.3.5](#)).

Adverse events will be followed until resolved, stable, or until the subject's last study visit and final safety follow-up phone call 60 days (+ 3 days) after the last dose. or subject is lost to follow-up.

#### **8.3.2. Adverse Event Eliciting/Reporting**

During the AE reporting period, study site personnel will query each subject at each visit to actively solicit any AE occurring since the previous visit. All AEs will be collected in response to a general question about the subject's well-being and any possible changes from the BL or previous visit, but shall not be specifically solicited. There will be no directed questioning for any specific AE. This does not preclude the site from collecting and recording any AEs reported by the subject to site personnel at any other time.

Whenever is possible, diagnoses should be recorded when signs and symptoms are due to a common etiology, as determined by qualified medical study staff.

New indications for medications started during the AE reporting period (i.e., after informed consent is obtained until 4 weeks after the last dose of study drug) will be recorded as AEs; recurrence or worsening of medical history problems requiring new or changes in concomitant medication, will also be recorded as AEs. Clinically significant laboratory results, physical examination findings, and ECGs will be recorded as AEs if they are deemed by the Investigator to meet the specified criteria.

The following attributes must be assigned to each AE:

- Description (Investigator's verbatim term describing the event)
- Dates of onset and resolution
- Severity
- Relationship to study drug
- Outcome
- Action taken regarding study drug
- Other treatment required

- Determination of “seriousness”

### 8.3.3. Assessing Adverse Event Severity

AEs, including abnormal clinical laboratory values, should be graded using the National Cancer Institute (NCI) Common Terminology Criteria for AE (CTCAE) v 4.0 guidelines. For terms not specified as part of NCI CTCAE, the following guidelines should be used to determine grade:

All AEs will be assessed for severity using the following criteria:

- **Grade 1, Mild:** Asymptomatic or mild symptoms which the subject finds easily tolerated. The event is of little concern to the subject and/or of little-or-no clinical significance; intervention not indicated.
- **Grade 2, Moderate:** The subject has enough discomfort to cause interference with or change in some of their age-appropriate instrumental activities of daily living (e.g., preparing meals, shopping for groceries or clothes, using the telephone, managing money); local or noninvasive intervention indicated.
- **Grade 3, Severe:** The subject is incapacitated and unable to work or participate in many or all usual activities. The event is of definite concern to the subject and/or poses substantial risk to the subject’s health or well-being; ; likely to require medical intervention and/or close follow-up, including but not limited to hospitalization or prolongation of hospitalization.
- **Grade 4, Life-threatening:** The subject was at immediate risk of death from the event as it occurred.
- **Grade 5, Death:** Fatal AE.

### 8.3.4. Assessing the Adverse Event’s Relationship to Study Drug

Most of the information about the safety of a drug prior to marketing comes from clinical trials; therefore, AE reports from investigators are critically important. The assessment of whether an AE is causally related to the study drug(s) using an evidence-based approach is critical in order to appropriately describe the safety profile study drug(s). Default reporting of individual events as possibly related is uninformative and does not meaningfully contribute to the development of the study drug’s safety profile.

The investigator must provide an evidence-based assessment of the relationship of the AE to study drug in accordance with the guidance below. Absence of an alternative cause would not normally be considered sufficient evidence to assess an event as related to study drug.

- Related:
  - Any event for which there is sufficient evidence to suggest that the study drug may have caused the event. For example, an unanticipated medical condition occurs which resolves with study drug interruption and re- occurs with re-administration of study drug; another example is a typical drug-related medical condition such as a rash that occurred shortly after first dose of study drug.

- Not Related:
  - The event represents a pre-existing underlying disease that has not worsened on study
  - The event has the same characteristics of a known side-effect associated with a co-medication
  - The event is an anticipated medical condition of anticipated severity for the study population
  - The most plausible explanation for the event is a factor that is independent of exposure to study drug

### **8.3.5. Reporting Serious Adverse Events on the SAE Report Form**

An SAE must be reported to the Sponsor and/or its designated safety management vendor within 24 hours of becoming aware of the SAE.

To report an SAE, the investigator must complete an SAE Report Form and fax or email the completed form to the Sponsor or its designated safety management vendor.

Full details of the SAE should also be recorded on the medical records and in the CRF. The following minimum information is required:

- Subject number, sex and age
- The date of report
- A description of the SAE (event, seriousness of the event)
- Causal relationship to the study drug

Follow-up information for the event should be sent promptly.

For each SAE observed, the investigator should obtain all of the information available about the event, including (but not limited to): hospital discharge diagnoses, hospital discharge note, death certificate, appropriate laboratory findings (including autopsies and biopsy results), and clinical examinations (including radiological examinations and clinical consultations).

The contact information for SAE reporting is as follows:

U.S. Toll-Free [contact]-Email: FibroGen\[contact]

#### **8.3.5.1. Reporting Serious Adverse Events to the Institutional Review Board / Independent Ethics Committee**

The investigator is responsible for notifying his/her Institutional Review Board (IRB) or Ethics Committee (EC) of SAEs in accordance with local regulations. The Sponsor, or its designated safety vendor, will provide a copy of expedited safety reports to the investigator that it intends to submit to global regulatory authorities.

### 8.3.5.2. Deaths

The investigator will report the fatal or life-threatening event immediately to the Sponsor's medical monitor. The investigator must provide a causal assessment of the relationship of the event to the study drug according to the guidance in [Section 8.3.5](#).

If the death occurred within the AE collection and reporting period (signed ICF to 4 weeks after last dose) and meets the reporting criteria, the investigator must submit the SAE Report Form in the same manner as described above in Section 8.3.5. Additionally, the site must complete the appropriate CRF page.

### 8.3.6. Pregnancies: Reporting and Follow-up of Subjects

The outcome of all pregnancies should be followed up and documented as described. Consent must be obtained from male subject's partner to collect information related to the pregnancy and outcome (and will be handled on a case-by-case basis with IRB/IEC approval). A Pregnancy Report Form must be completed and submitted to Sponsor or designated safety management vendor within 24 hours of the investigator becoming aware of the pregnancy. The investigator must follow-up to completion of the pregnancy to ascertain its outcome (e.g., spontaneous miscarriage, elective termination, ectopic pregnancy, normal birth or congenital abnormality) and whether any AEs occur during the pregnancy or birth. The outcome of the pregnancy must be reported by the investigator on a Pregnancy Outcome Report Form, which should be sent to the Sponsor and/or its designated safety vendor within 24 hours of the investigator becoming aware of the outcome.

### 8.3.7. Abnormal Laboratory Findings

An abnormal laboratory finding in absence of any other signs or symptoms is not necessarily an AE. The investigator must review and assess all laboratory results throughout the study in a timely manner, and determine whether any abnormal laboratory values, if any, are clinically significant (CS) or not clinically significant (NCS), and whether there are associated signs and symptoms. Clinically significant laboratory abnormalities will be reported as AEs. Laboratory abnormalities should be considered clinically significant when they occur after taking study medication, reflect a meaningful change from the screening value(s), and require active management (e.g., abnormalities that require study treatment dose modification, discontinuation, more frequent follow-up assessments, etc.).

If the abnormal laboratory finding is accompanied by signs or symptoms, report the signs and symptoms as the AE in lieu of the abnormal laboratory value. If a diagnosis is available, report the diagnosis.

## 9. STATISTICAL CONSIDERATIONS

### 9.1. Sample Size Determination

This study tests the hypothesis of whether pamrevlumab can attenuate the annual decline from baseline to Week 104 in FVC in non-ambulatory DMD patients. A total of 22 subjects is planned to achieve 80% power to test the null hypothesis of change in percent predicted FVC of -5% against the alternative hypothesis, assuming a mean change of -2% and standard deviation of 5% based on 2-sided one sample t-test at 0.05 significance level. The hypotheses are:

H0: change in percent predicted FVC less than or equal to -5%

Ha: change in percent predicted FVC greater than -5%.

The primary efficacy endpoint will be met if the annual change in percent predicted FVC is greater than -5% at the end of the study (lower bound of 2-sided 95% confidence interval is greater than -5%).

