## STATISTICAL METHODS

A total of 22 subjects is planned to achieve 80% power to test the null hypothesis of change in percent predicted FVC of -5% against the alternative hypothesis, assuming a mean change of -2% and standard deviation of 5%, based on a 2-sided one sample t-test at 0.05 significance level.

The primary efficacy endpoint will be met if the annual change in percent predicted FVC is above -5% after 104 weeks of treatment with pamrevlumab (lower bound of the 2-sided 95% confidence interval is above -5%).

An interim analysis will be conducted after at least 10 to 12 subjects have completed 1 year of treatment. As a result, sample size may be readjusted to a total of approximately 32 subjects.

The primary efficacy endpoint is the annual change from baseline to Week 104 in percent predicted FVC during treatment with pamrevlumab. The mean annual change in percent predicted FVC and the corresponding 2-sided 95% confidence interval will be presented.

Final analysis of the primary and secondary endpoints will be described in the statistical analysis plan. Details of the interim analysis will be described in an interim analysis plan.

Pamrevlumab concentrations and derived PK parameters will be tabulated and summarized using descriptive statistics. Descriptive statistics (number of subjects, mean, geometric mean, standard deviation, minimum, maximum, and coefficient of variation) will be presented for the PK parameters. Attainment of steady-state will be investigated.

Safety analyses will include summary of adverse events (including treatment emergent AEs, treatment emergent serious AEs, deaths, and infusion-associated AEs), prior and concomitant medication use, measurements of laboratory tests, vital signs, and electrocardiograms (ECGs), and physical exams.

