## 5.4. Replacement of Subjects

Subjects may be replaced in this study if a subject's participation is not terminated due to safety or tolerability issues and is replaced prior to completion of targeted recruitment into the study. Replacement decisions will be made between the sponsor and investigator on a case-by-case basis.

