#### 9.2.2. Full Analysis Set Population

The Full Analysis Set Population (FAS) will consist of all subjects in the Safety Population who have at least one evaluable post-baseline FVC assessment.

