### **9.4.1. Primary Endpoint**

The primary endpoint is the annual change from baseline to Week 104 in percent predicted FVC during treatment with pamrevlumab. The mean annual change in percent predicted FVC and the corresponding 2-sided 95% confidence interval will be presented. The primary efficacy endpoint will be met if the lower bound of 2-sided 95% confidence interval is greater than -5%.

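### With 22 subjects, the two-sided one-sample t-test named in the protocol has 76.5% power, not the stated 80%, which matches the normal approximation

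*Protocol*

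**What the plan says.** Protocol section 9.1 gives the whole sample size argument in one sentence: "A total of 22 subjects is planned to achieve 80% power to test the null hypothesis of change in percent predicted FVC of -5" percent, "assuming a mean change of -2% and standard deviation of 5" percent. It names the test in the same sentence: "standard deviation of 5% based on 2-sided one sample t-test at 0.05 significance level". Under Statistical Methods, the synopsis repeats the claim with the same inputs: "A total of 22 subjects is planned to achieve 80% power".

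Section 9.4.1 sets the success rule: "The primary efficacy endpoint will be met if the lower bound of 2-sided 95% confidence interval is greater than -5" percent.

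Neither sample size statement names the formula or software used, and neither gives a dropout allowance. The synopsis and section 4.2 add that an interim analysis, once 10 to 12 subjects have completed a year, may raise the total to about 32.

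**The concern.** The power figure is tied to a specific test, and at this sample size the choice between a t and a normal calculation matters. With 21 degrees of freedom the two-sided 5% critical value is 2.080, against 1.960 for the normal distribution, and the standard deviation has to be estimated from 22 observations. A calculation that ignores this overstates the power.

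What is at stake is the stated chance of a false-negative result. A reader who takes the 80% at face value will think that a true mean change of -2% would be missed in one trial in five. Under the protocol's own assumptions the risk is higher.

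**Working it through.** **Inputs, all from protocol section 9.1:** n = 22; null mean -5; alternative mean -2; standard deviation 5; two-sided alpha 0.05; one-sample t-test. The difference is 3 and the standardised effect is 3/5 = 0.6.

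**Step 1. Reproduce the plan's figure.** The normal-approximation formula is n = [SD × (z₀.₉₇₅ + z₀.₈₀) / difference]².

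- n = [5 × (1.960 + 0.842) / 3]² = 21.80, rounded up to 22.
- Power at 22 = Φ(0.6 × √22 − 1.960) = Φ(2.814 − 1.960) = 80.35%.

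This recovers both the 22 and the 80%. A one-sided test at 0.05 does not: at n = 22 it gives 85.9% by t and 87.9% by z. A slip in sidedness therefore does not explain the stated figure.

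**Step 2. Power of the named test.** Power is the probability that a noncentral t variable, with n − 1 degrees of freedom and noncentrality 0.6 × √n, falls beyond the two-sided 5% critical values. At n = 22 there are 21 degrees of freedom, the noncentrality is 2.814 and the critical value is 2.080.

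| n | Power, two-sided t-test | Power, normal approximation |
|---|---|---|
| 22 | 76.5% | 80.4% |
| 23 | 78.5% | 82.1% |
| 24 | 80.4% | 83.6% |
| 32 | 90.8% | 92.4% |

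The shortfall at 22 is 80 − 76.5 = 3.5 percentage points, and the type II error is 100 − 76.5 = 23.5%. The smallest n with at least 80% power is 24.

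**Step 3. Check against the success rule.** One million trials of 22 observations were simulated from a normal distribution with mean -2 and standard deviation 5. The lower limit of the two-sided 95% t interval was above -5 in 76.6% of them, in agreement with step 2.

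**Step 4. The same gap on the FVC scale.** Suppose that 22 subjects are analysed and the observed standard deviation is 5.

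- Half-width by t: 2.080 × 5/√22 = 2.22, so the observed mean must exceed -5 + 2.22 = -2.78.
- Half-width by z: 1.960 × 5/√22 = 2.09, so the observed mean would have to exceed only -5 + 2.09 = -2.91.

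**Step 5. What would make 80% correct at 22.** The standardised effect would have to be 0.6264. That means a standard deviation of 3/0.6264 = 4.79, or a difference of 0.6264 × 5 = 3.13.

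**The case against.** The case against giving this weight has four parts.

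- **The sample size may rise.** With 32 subjects the t-test has 90.8% power. The rule for the increase is left to a separate interim analysis plan that is not among the documents, so the power of the whole design cannot be computed. This stands as a limit on the consequence: the 23.5% miss rate applies if the number stays at 22. It does not rescue the 80%, which is claimed for 22, because the increase is only a possibility.
- **The gap is small.** It amounts to two subjects, other parts of the protocol speak of approximately 22, and a standard deviation of 4.79 would close it. No source is cited for the value of 5, and uncertainty in it could easily outweigh 3.5 points. That is a fair view of its importance, but the stated figure still does not follow from the stated inputs.
- **Little now depends on it.** The SAP addendum (section 1) reports database lock and a completed interim study report, the primary objective is one of estimation, and section 9.5 describes the study as exploratory. A result can be judged from its confidence interval. It remains true that section 9.1 sets a formal success criterion with a stated power, and that reporting is still open: the extension SAP (section 1.2) says that the extension data will go into the clinical study report.
- **The source of the 80% is inferred.** No document says that the normal approximation was used. It was the only variant tried that gave 80% at 22, but the 76.5% does not depend on that explanation.

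The final analysis may also be a model rather than a t-test. The main-study SAP, version 1.0, is named in the addendum but is not among the documents, so nothing is claimed here about the power of that model.

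**Conclusion.** The concern holds: the stated power is wrong for the stated test. Under the protocol's own inputs, 22 subjects give 76.5% power, and 24 are the fewest that give 80%. The error is modest and affects only the description of the design. The type I error, the interval and the success rule stand as written.

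The figure assumes normally distributed changes, 22 subjects contributing to the analysis and no increase after the interim. Fewer contributors would lower it: as an assumed illustration only, 20 give 72.1% and 18 give 67.0%. Dropout need not reduce the number one for one, because the full analysis set in section 9.2.2 keeps "all subjects in the Safety Population who have at least one evaluable post-baseline FVC assessment", and section 5.4 allows limited replacement.

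**What to change.** In protocol section 9.1 and the synopsis, or wherever the design is next reported, replace the power claim with a statement to this effect: *22 analysed subjects give about 77% power for a two-sided one-sample t-test at alpha 0.05, assuming a mean change of -2% against a null of -5% and a standard deviation of 5%.*

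This costs one sentence in two places and a slightly less favourable figure. Enrolment, endpoint, analysis and success rule do not change.
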